6.5.2. Criteria for Permanent Discontinuation of Study Cream

Participants must permanently discontinue study cream if they meet any of the following criteria:

- Occurrence of an AE that is related to treatment with the study cream that, in the judgment of the investigator or the medical monitor, compromises the participant's ability to continue study-specific procedures or is considered to not be in the participant's best interest
- Worsening of AD that requires treatment with a prohibited concomitant medication
- Any Grade 4 laboratory abnormality (see [Table 7](#)) considered related to the study cream
- Persistent AE requiring an interruption of study cream for more than 2 weeks without resolution of the AE

See Section [7](#) for discontinuation procedures.

6.6. Prior and Concomitant Medications and Procedures

All concomitant medications and treatments (including over-the-counter or prescription medicines, vitamins, vaccines, and/or herbal supplements) must be recorded in the eCRF. Any prior medication received up to 28 days before the first application of study cream and any new or ongoing medication used during the study through 30 days after the last application of study cream will be recorded in the eCRF. Any addition, deletion, or change in the dose of these medications will also be recorded.

Concomitant medications administered beyond 30 days after the last application of study cream should only be recorded for SAEs. Concomitant treatments/procedures that are required to manage a participant's medical condition during the study will also be recorded in the eCRF. The medical monitor should be contacted if there are any questions regarding concomitant or prior therapy.

6.6.1. Prior Therapies for Treatment of Atopic Dermatitis

Acceptable documentation of recent history with TCSs and TCIs or, when appropriate, systemic treatments must be collected by the investigator or a qualified designee at the screening visit and must include treatment details (eg, name, start/end dates, regimen) and treatment outcome (eg, inadequate response, intolerance). For instances in which a topical agent was not restarted due to prior intolerance (see Section 5.1, Inclusion Criterion 9), the reason for not restarting must also be recorded on the eCRF. The necessary information can be collected from one or more of the following sources and must be recorded and signed off in an investigator attestation:

- Communication with the participant's treating physician
- Documentation at the investigative site, such as the following:
 - Medical history records
 - Pharmacy records (with clearly listed dates of dispensation)
 - Hospital records
 - Participant interview

6.6.2. Permitted Medications and Procedures

The following are permitted during the study:

- Participants may use bland emollients (except those containing urea, salicylic acid, or lactic acid) such as Eucerin cream. Participants should continue to use the bland emollient/moisturizer in the same manner they did before entering the study and throughout the course of the study.

Note: Emollients should not be used within 4 hours before and 2 hours after application of study cream.

- Bathing during the study should be limited to once daily for no longer than 15 minutes and not within 2 hours following study cream application. During baths, tepid (not hot) water and mild cleansing agents (eg, Basis bar or Dove) should be used. Showers should be limited in time with warm water and mild cleansing agents should be used.
- If sunscreen is needed, a mineral-based sunscreen (such as zinc oxide– or titanium oxide–based) with an SPF of at least 30 may be used not less than 4 hours before and at least 2 hours after study cream application.
- Participants may use nonsedating, over-the-counter antihistamines.

6.6.3. Restricted Medications and Procedures

The following are permitted during the study under specified conditions:

- Short-term use of systemic corticosteroids may be permitted to treat acute AEs (eg, asthma) during the VCE period, and the decision to keep the participant in the study (or to permanently discontinue study cream) will be made in consultation with the medical monitor and sponsor.
- Participants may continue using sedating antihistaminic drugs, as long as their use is part of a pre-existing, well-established, and stable treatment regimen, 2 weeks prior to Day 1 and throughout the first 8 weeks of study. There are no restrictions for use of nonsedating antihistamines.
- Use of any over-the-counter, nonprescription preparations deemed acceptable by the investigator is permitted under an established and stable treatment regimen 2 weeks prior to Day 1 and throughout the first 8 weeks of the study.
- Use of any prescription medication (including phytotherapeutic, herbal, or plant-derived preparations) within 2 weeks before Day 1 through the safety follow-up visit is allowed if deemed acceptable by the investigator.
- Immunizations with a live-attenuated vaccine are not recommended during the VC and VCE periods unless deemed necessary by the investigator.
- Allergen immunotherapy (desensitization) that is ongoing at a stable dose at the time of study entry may be continued while on study but only at the same dose throughout the first 8 weeks of the study.
- Bleach baths are allowed as long as they do not exceed 2 baths per week and their frequency remains the same throughout the first 8 weeks of the study.
- Topical anti-infectives or other topical treatments applied to active AD lesions should not be used for at least 4 hours before and 2 hours after application of study cream.

6.6.4. Prohibited Medications and Procedures

The following are not permitted during screening or the VC/VCE periods:

- Any investigational medication other than the study cream
- Any of the following topical treatments: corticosteroids, calcineurin inhibitors, PDE4 inhibitors, or aryl hydrocarbon receptor–modulating agents
- Other topical agents for treatment of AD (except bland emollients as noted in Section [6.6.2](#))
- Treatment known to affect the course of AD
- Systemic corticosteroids, methotrexate, cyclosporin A, azathioprine, biologic therapies, or other immunosuppressant agents
- Phototherapy or tanning beds
- Strong systemic CYP3A4 inhibitors

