^b For prior medications that require a 4-week washout period (see Section 5.2, Exclusion Criterion 5b), a 35-day screening period is allowed.

^c Day 1 visit should be scheduled and conducted in the morning (AM). The current Itch eDiary assessments at timepoints up to and including 60 minutes post-study cream application are required to be performed on-site.

^d Week 8 is the baseline for participants eligible to continue in the VCE period ($BSA \leq 20\%$).

Table 4: Schedule of Activities: Vehicle-Controlled Extension Period/Escape Arm

Visit (Range)	VCE Period ^a		Safety Follow-Up	Notes
	Weeks 12, 16, and 20 (± 7 d)	Week 24/EOT or ET2 (± 7 d)	30 Days (+ 7 d) After Week 24 or ET Visit	
Administrative procedures				
Contact IRT	X	X		Section 8.1.3 .
Concomitant medications and procedures	X	X	X	Section 6.6 .
Apply study cream at site under direct site staff supervision	X			Section 6.1.1 . Only for participants with active AD lesions at time of visit.
Weigh/dispense study cream	X			Section 6.4 . New tubes of study cream will be provided at each visit.
Collect/weigh returned study cream and review eDiary	X	X		Section 6.4 .
Assess study cream compliance	X	X		Section 6.4 .
Contact participant to confirm compliance with eDiary	X*			Section 6.4 and Section 8.1.4 . *Telephone call contact should occur between regularly scheduled visits (eg, Weeks 10, 14, 18, and 22) to ensure compliance with the eDiary. AEs and concomitant medications can be recorded as well.
Safety assessments				
AE assessments	X	X	X	Section 8.3.1 and Section 9 .
Targeted physical examination	X	X	X	Section 8.3.2.2 . Conducted only when indicated by symptoms reported by the participant, AEs, or other findings; clinically significant abnormalities (in the investigator's judgment) are to be reported as AEs.
Comprehensive physical examination		X*		Section 8.3.2.1 . *ET2 visit only.
Body weight	X	X	X	Section 8.3.3 .
Vital signs	X	X	X	Section 8.3.3 . To be taken before blood sampling and other procedures (not including PROs).

Table 4: Schedule of Activities: Vehicle-Controlled Extension Period/Escape Arm (Continued)

Visit (Range)	VCE Period ^a		Safety Follow-Up	Notes
	Weeks 12, 16, and 20 (± 7 d)	Week 24/EOT or ET2 (± 7 d)	30 Days (+ 7 d) After Week 24 or ET Visit	
PRO assessments				

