10. Agree to discontinue all agents used to treat AD from screening through the final follow-up visit, except as outlined in Section 6.6.2 and Section 6.6.3.
11. Willingness to avoid pregnancy, breastfeeding, or fathering children based on the criteria below.
- a. Male participants with reproductive potential must agree to take appropriate precautions to avoid fathering children from screening through 90 days (a spermatogenesis cycle) after the last application of study cream and must refrain from donating sperm during this period. Permitted methods in preventing pregnancy should be communicated to the participants and their understanding confirmed (see [Appendix A](#)).
 - b. Female participants who are WOCBP must not be lactating or breastfeeding and have a negative serum pregnancy test at screening and a negative urine pregnancy test before the first application of study cream on Day 1 and must agree to take appropriate precautions to avoid pregnancy from screening through 30 days (1 menstrual cycle) after the last application of study cream and must refrain from donating oocytes during this period. Permitted methods in preventing pregnancy (see [Appendix A](#)) should be communicated to the participants and their understanding confirmed.
 - c. Female participants not considered to be of childbearing potential are eligible (see [Appendix A](#)).
12. Ability to comprehend and willingness to sign an ICF. (Note: A signed written ICF must be obtained for inclusion; see Section 8.1.1.)

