If there are new areas to be treated, including expansion of existing areas or development of new areas, after consultation with the investigator, study cream should be applied to these areas in addition to the areas identified at the baseline visit (up to a maximum total of 20% BSA) for the remainder of the VC period, and the percentage of BSA to be treated will be recalculated and increased accordingly. This new estimate will be entered into the IRT system to calculate the number of tubes of study cream to be dispensed. During the VC period, participants whose additional new areas to be treated in addition to the areas identified at the baseline visit exceed 20% BSA will be discontinued from study treatment and complete the ET visit.

The VCE period starts at the Week 8 visit and completes at the Week 24 visit, with the final possible application being the evening application on the day before the Week 24 visit. During the VCE period, only areas with active disease should be treated.

After completing 8 weeks of continuous treatment, all eligible participants with an adequate response, defined as achieving at least EASI50 from baseline, will continue their blinded treatment allocation and will be evaluated during an additional 16-week VCE period for durability of response. Participants will be eligible to enter the ruxolitinib 1.5% cream open-label escape arm if EASI50 is not achieved at Week 8 or if an EASI50 response from baseline is lost during the VCE period. (Note: < EASI50 must be observed at 2 consecutive visits, one of which can be an unscheduled visit, at least 1 week apart.)

The start and end dates of treatment applications will be captured by the participant. Once the lesions clear (IGA score of 0), participants should continue to apply study cream for an additional 3 days to the areas of the body where lesions were last present before discontinuing treatment. Following clearance, if a lesion recurs, treatment should be resumed at the first sign of recurrence.

At any time during the VCE period, if a participant's total AD-affected area exceeds 20% BSA, the participant will be discontinued from study treatment and complete the ET visit.

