#### **7.5.2.4. Analysis of Desensitization and Rebound in the VCE DB Period**

The following categorical parameters will be summarized by treatment to assess rebound upon treatment cessation:

- Proportion of participants who experience a relapse after study treatment discontinuation. (ie, proportion of participants among EASI75 responders who are on study treatment at Week 24 who meet relapse criteria [loss of EASI50 from baseline] at the safety follow-up visit)

[figure not shown]
The following endpoints will be summarized by treatment and visit to assess desensitization upon treatment cessation:

[figure not shown]
[figure not shown]
- Proportion of time off study treatment due to lesion clearance during the VCE period by visit
- Proportion of time on study treatment during the VCE period by visit

Time to first re-treatment is defined as the interval between the first interruption due to lesion clearance starting from Week 8 to the end of the VCE period and the time of starting the re-treatment. This analysis will be performed in the VCE re-treatment evaluable population as defined in Section 5.3.7. The Kaplan-Meier estimate of median time to first re-treatment will be presented with its 95% CI. The 95% CI will be calculated using the method by Brookmeyer and Crowley (1982).

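### Rules on AD therapy after Week 24 conflict, recording can stop before the relapse visit, and a relapse treated back to EASI50 counts as no relapse

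*Protocol*

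**What the plan says.** **Endpoint.** SAP 7.5.2.4 and the protocol's Table 5 define relapse among EASI75 responders on study treatment at Week 24. The event is counted for those "who meet relapse criteria [loss of EASI50 from baseline] at the safety follow-up visit". SAP 7.5.2.4 lists this result among those used to assess rebound when treatment stops.

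**Rules on AD therapy in the follow-up month.** Three passages of the protocol bear on it:
- Section 5.1, inclusion criterion 10: participants "Agree to discontinue all agents used to treat AD from screening through the final follow-up visit", except as Sections 6.6.2 and 6.6.3 allow.
- Section 6.6.4: the prohibited list begins "The following are not permitted during screening or the VC/VCE periods". Section 6.1 fixes where that stops: "The VCE period starts at the Week 8 visit and completes at the Week 24 visit".
- Section 6.6.3: prescription medication from 2 weeks before Day 1 "through the safety follow-up visit is allowed if deemed acceptable by the investigator".

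**Recording.** Section 6.6 says "Concomitant medications administered beyond 30 days after the last application of study cream should only be recorded for SAEs". Table 4, however, marks concomitant medications and procedures at the safety follow-up visit.

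**Analysis.** Neither document says how AD therapy started between the last application and the follow-up EASI is handled. The estimand tables cover only the coprimary endpoints. SAP 6.6 summarizes AD concomitant medication for the VC and VCE periods, and Appendix A adds the escape arm. No summary for the follow-up period is named.

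**The concern.** The participants most likely to start another AD treatment after stopping the cream are those whose disease returns. If that treatment brings them back to EASI50 by the follow-up visit, the definition classes them as not relapsed. New therapy in this window is foreseeable. Protocol 4.1 asks investigators to consider alternatives, including systemic therapy, at or after Week 8 when severity criteria are met, and gives no end date. Section 8.7 allows unscheduled visits whenever medically warranted.

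At stake is a result read as evidence on what happens after the cream stops. Successful treatment of a flare moves it in one direction only, toward reassurance. Sites may also apply different rules, because the passages can be read differently, and the records that would show who was treated may stop short of the visit.

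**Working it through.** The plan gives no relapse rate or follow-up treatment rate, so there is no plan figure to reproduce. The check is calendar arithmetic, a comparison of passages, and an illustration on assumed values.

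**1. Timing.** Take the Week 24 visit as day 0.
- Last possible application (Protocol 6.1): "with the final possible application being the evening application on the day before the Week 24 visit", so day -1.
- Follow-up visit (Table 4): "30 Days (+ 7 d) After Week 24 or ET Visit", so day 30 to day 37.
- Recording limit (Protocol 6.6): 30 days after the last application, so day -1 + 30 = day 29.

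Interval from last application to relapse visit: 30 - (-1) = 31 days, up to 37 - (-1) = 38 days.

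Unrecorded tail: 31 - 30 = 1 day, up to 38 - 30 = 8 days. As a share of the interval this is 1/31 = 3% to 8/38 = 21%. The first 30 days are recorded.

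A participant who stopped cream 7 days earlier has 38 to 45 days, of which 8 to 15 are unrecorded. Such a participant falls outside the endpoint text, which requires being on treatment at Week 24. The population stated for SAP Table 2.14.1 does not carry that requirement.

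**2. Passages side by side.**

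| Passage | Period covered | Reaches the relapse visit? |
|---|---|---|
| Criterion 10 | Screening to final follow-up visit, with exceptions | Yes |
| Section 6.6.4 | Screening, VC and VCE | No, VCE ends at Week 24 |
| Section 6.6.3, prescription medication | 2 weeks before Day 1 to follow-up, at investigator's judgment | Yes, as a permission |
| Section 6.6, recording | To 30 days after last application, then SAEs only | No, short by 1 to 8 days |
| Table 4, concomitant medications | Marked at the follow-up visit | Yes |

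The first three disagree on restriction, and the last two on recording.

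**3. Direction and possible size.** Let r be the proportion who would relapse untreated and m the share of those relapses that are treated and back at EASI50 by the visit. Then observed relapse = r x (1 - m). Since m cannot be negative, the observed rate cannot exceed r. Both r and m are assumptions:

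| r | m = 10% | m = 25% | m = 50% |
|---|---|---|---|
| 20% | 18% | 15% | 10% |
| 40% | 36% | 30% | 20% |
| 60% | 54% | 45% | 30% |

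For example, 40% x (1 - 0.25) = 30%. Nothing in the documents says which cell applies.

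**The case against.** The other side has several good points.

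- **A restriction exists after Week 24.** A reader of Section 6.6.4 alone might infer that AD therapy is free from that visit on. Criterion 10 does not support this. The defect is inconsistent wording, not an absent rule.
- **The prescription clause may be general.** If Section 6.6.3 licensed AD drugs in follow-up, it would license them in the VC and VCE periods too and empty Section 6.6.4. The coherent reading is ordinary medication subject to the AD restrictions. This is a fair argument, but criterion 10 names 6.6.3 as an exception, so the text does not settle it.
- **Most treatment would be seen.** The first 30 days are recorded, Table 4 schedules medications at the visit, and Section 6.6 separately asks for treatments needed to manage a medical condition during the study. Therapy begun in the last 1 to 8 days also has the least time to restore EASI50. This stands: the recording gap is the smaller part. The larger part is that no rule uses the records.
- **Counting every therapy start as relapse can err upward.** Section 6.7 provides no treatment after the study, so some participants may resume usual care while still at EASI50. That is a different estimand. It stands as a reason to keep such a rate supplementary.
- **The endpoint is minor.** It is outside the testing hierarchy and only summarized by treatment. This limits the weight of the point but does not remove it.

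**Conclusion.** The concern holds in a limited form. The passages on AD therapy between Week 24 and the follow-up visit conflict. Read literally, Section 6.6 ends non-SAE recording 1 to 8 days before the relapse assessment for a participant who applies cream until the evening before Week 24, and Table 4 contradicts it. The relapse definition takes no account of AD therapy started after the cream stops, so a relapse treated back to EASI50 is counted as none. The effect can only lower the reported rate.

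Three stronger conclusions are not supported:
- It does not follow that all treated relapses are missed. A treated participant still below EASI50 at the visit counts as relapsed.
- It does not follow that such therapy cannot be identified, since all but the last 1 to 8 days are recorded even on the narrow reading.
- It cannot be said that this is the only planned look at disease after stopping. SAP 7.1 extends by-visit analyses, EASI included, to the safety follow-up, and part of SAP 7.5.2.4 is not visible in the public text.

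The size of the bias is unknown, because the relapse and treatment rates used above are assumptions. The coprimary and key secondary tests are unaffected.

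**What to change.** 1. **Protocol 6.6:** record concomitant medications and procedures through the safety follow-up visit, consistent with Table 4. The unrecorded tail of 1 to 8 days then falls to 0. The visit already collects these data, so the cost is a sentence and an eCRF guideline change.
2. **SAP 7.5.2.4 and Table 2.14.1:** keep the EASI-only relapse rate. Beside it, show a supplementary rate that also counts as relapsed anyone who starts a therapy on the Section 6.6.4 list after the last application and before the follow-up EASI. Report the number starting such therapy by arm. The cost is a short SAP rule and extra table rows. The supplementary rate may overcount participants who resume therapy without losing EASI50, and the two rates should be read together for that reason.
3. **Protocol 5.1 (criterion 10), 6.6.3 and 6.6.4:** reconcile the period each covers. Which rule should apply is for the sponsor to decide and is not judged here.

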6.7. Treatment After the End of the Study

There will be no treatment provided after the end of the study.

7. DISCONTINUATION OF STUDY TREATMENT AND PARTICIPANT WITHDRAWAL

7.1. Discontinuation of Study Treatment

7.1.1. Reasons for Discontinuation

Participants **must** be discontinued from study treatment for the following reasons:

- Lack of efficacy response during the VCE period (defined as no change/improvement in %BSA, IGA score, or EASI score when treated with ruxolitinib cream in the escape arm continuously for 8 weeks).
- AD worsens during either the VC period or the VCE period (including the escape arm), to the point where the extent of AD to be treated (ie, all areas excluding the scalp) exceeds 20% BSA.
- The participant becomes pregnant.
- Consent is withdrawn.

Note: Consent withdrawn means that the participant has explicitly indicated that they do not want to be followed any longer; in this case, no further data, except data in the public domain, may be solicited from or collected on the participant. Participants may choose to discontinue study treatment and remain in the study to be followed for safety monitoring.

- Further participation would be injurious to the participant's health or well-being, in the investigator's medical judgment.
- Any AE of unacceptable severity as noted in Section 6.5.2.
- The study is terminated by the sponsor.
- The study is terminated by the local health authority, IRB, or IEC.

A participant **may** be discontinued from study treatment as follows:

- Participants who are noncompliant with study cream (see Section 6.4) or who use more than one 60-g tube per 4 days will have the application instructions reinforced by the investigator or a qualified designee. Participants who after 2 consecutive study visits and reinforcement of study cream application instructions by site staff again fail to meet compliance benchmarks or again use more than one 60-g tube per 4 days may be considered for withdrawal from the study. The medical monitor should be consulted for instruction on handling the participant.
- If, during the course of the study, a participant is found not to have met eligibility criteria, the sponsor's medical monitor or delegate, in collaboration with the investigator, will determine whether the participant should be withdrawn from study treatment.
- If a participant is noncompliant with study procedures (eg, completion of eDiary), the sponsor's medical monitor (or designee) should be consulted for instruction on handling the participant.

